## RELATIONSHIP BETWEEN FIBRINOGEN AND RISK OF ADVERSE COPD OUTCOMES

### Objectives

The primary purpose of this analysis is to assess the relationship between plasma fibrinogen concentration and adverse COPD clinical outcomes within varying time points that are relevant to a conduct of a clinical trial, and to support the Cox models described later. The association between fibrinogen levels and COPD exacerbations will be evaluated at time points of 12 months and 18 months. The association between fibrinogen levels and mortality will be evaluated at time points of 2 years and 3 years. The nature of the relationship will be critical to the determination of an appropriate cut-point or threshold defining “high” fibrinogen.

These analyses will:

- Define a cut-point for patients with high fibrinogen
- Describe and compare patients with high fibrinogen and patients with low fibrinogen according to demographic characteristics and covariates
- Assess the relation between high fibrinogen and the risk of COPD exacerbations within 12 and 18 months and mortality within 2 and 3 years
  - Identify predictors using recommended cut points
- Assess the time-to-event (COPD exacerbation and/or all-cause mortality) among patients with high fibrinogen
- Assess the impact of fibrinogen on the sample size of a hypothetical clinical trial

### Proposed Analyses

1. Assess the time-varying relationship between high fibrinogen and the risk of adverse COPD outcomes.

*Analysis:*

Cox proportional hazards models will be used to identify hazard risk ratios with corresponding 95% confidence intervals associated with fibrinogen levels as well as demographic and clinical characteristics. These models will account for the time-varying nature of the relationship between fibrinogen levels and exacerbations/all-cause mortality; as such, they can only be performed in studies that recorded the dates of outcomes of interest. There will be two main groups considered in the modeling process:

1. Age 40+, GOLD stage 2+, history of exacerbations unspecified
2. Age 40+, GOLD stage 2+, and any prior COPD exacerbation (ECLIPSE)

Analyses using hospitalized exacerbations as an endpoint will be completed for outcomes which are recorded within 12 months of the initial fibrinogen measurement. Analyses with mortality will be completed for outcomes which are recorded within 3 years of the initial fibrinogen measurement. Analyses will be conducted using the fibrinogen thresholds determined previously (250 mg/dL, 300 mg/dL, 350 mg/dL, and 400 mg/dL).

Each outcome model will be constructed as follows:

1. The association between baseline characteristics and each outcome will be examined using univariate models. These models will be fitted on data of patients with high and low fibrinogen, and will result in a set of baseline characteristics that are predictive of the outcome and will be used as candidates for the final model.
2. To identify confounders of the cohort-outcome effect (e.g., the association between high vs. low fibrinogen and a given outcome), all baseline characteristics will be tested individually in a model with cohort as the only other independent variable. Those variables modifying the cohort-outcome effect size by at least 10% will create an additional set of candidates for the final model.
3. To obtain the fully adjusted model, the first step will be to add the candidate variables from step 2 to the unadjusted model one at a time, in descending order of strength of the confounder (i.e., the percentage change in the hazard ratio that results from adding that variable to the unadjusted model). Variables that still modify the cohort-outcome effect size by at least 10% will be retained, as will any that are significant predictors of the outcome at  $P < 0.05$ .
4. The second step in constructing the fully adjusted model will be to take the model resulting from step 3, which will include all of the confounders and significant predictors forced into the model. Into that model, all of the significant predictor variables identified in step 1 that were not tested in step 3 will be entered and backward selection with  $P < 0.05$  used to select from among these additional variables. This will allow inclusion of significant predictors in the model that do not necessarily act as confounders.
5. Finally, a correlation matrix will be created for all variables included in the model in step 4. If two or more variables are found to be highly correlated with one another (i.e., a correlation of 0.90 or greater), the variable that acts as the stronger confounder or the stronger predictor of the outcome will be selected and the other variable dropped from the model.

Hazard ratios and 95% confidence intervals will be presented for each of the final outcome models.

*Variables for consideration:*

- Demographic and clinical characteristics

1. Assess the relation between high fibrinogen and the risk of adverse COPD outcomes over time.

*Analysis:*

Time-to-event analyses will be performed using survival analysis methods for patients with high fibrinogen in studies which recorded dates of hospitalized exacerbations (ARIC, CHS, and ECLIPSE) and all-cause mortality (ARIC, CHS, ECLIPSE, FHS, and NHANES). PROC PHREG will be used to create Kaplan Meier plots for each outcome, and plots will be repeated for each threshold assessed. Means, standard deviations, medians, and ranges of time-to-events will also be calculated.

*Variables for consideration:*

- Demographic and clinical characteristics
2. Assess the impact of using a fibrinogen threshold to select patients at higher risk of outcomes on the sample size of a hypothetical clinical trial

*Analysis:*

Survival estimates from the Cox models produced for each outcome will be used to generate power analyses to present the sample sizes of a hypothetical clinical trial designed to assess hospitalized exacerbations within 12 months or mortality within 36 months. Sample sizes will be presented for each fibrinogen threshold and will also be presented for hazard ratios of 0.6, 0.7, and 0.8. This analysis will assume a power of 0.8 and a 10% loss to follow-up. Equal sample sizes will be assumed for both “control” and “treatment” groups.

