In an analysis combining subjects from the ARIC and CHS studies, Valvi et al. (2012) reported that mean plasma fibrinogen concentrations increased with increasing severity of COPD. Subjects whose plasma fibrinogen concentration was in the top decile for the cohort (>393.0 mg/dL) were at increased risk for COPD-related hospitalizations and death during follow-up (mean follow-up time of 9.7 years). This relation remained even after adjusting for potential confounders such as CVD (self-reported), age, gender, race, smoking status, and BMI. Mannino et al. (2012) recently reported the results of an analysis of participants in the NHANES III study. Participants with COPD, particularly GOLD stage defined stages 3 and 4 had higher plasma fibrinogen concentrations when compared to subjects with milder COPD or non-COPD subjects. Elevated plasma fibrinogen was associated with an increased risk for all-cause mortality. Information on COPD exacerbations/hospitalizations was not reported.

Although this prior research provides evidence of the association between high fibrinogen and COPD exacerbations, published literature is not currently available that would support the use of fibrinogen as a biomarker for increased risk of COPD-related outcomes during a time period that would be relevant to the conduct of a clinical trial. Moreover, the integration of 5 independently conducted studies will provide evidence regarding the robustness of fibrinogen as a biomarker of adverse COPD outcomes across various patient populations and time periods.

**These data present considerable evidence that plasma fibrinogen is closely related to COPD and COPD exacerbations, and support a formal quantitative assessment of plasma fibrinogen as an independent predictor of clinical endpoints in patients with COPD.**

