## Fibrinogen Classification

Based on preliminary analyses of the distribution of fibrinogen among patients with COPD, four thresholds of baseline fibrinogen will be assessed in these analyses: 250 mg/dL, 300 mg/dL, 350 mg/dL, and 400 mg/dL. The terms "high" and "low" fibrinogen will refer to the level of fibrinogen in relation to the threshold(s) being assessed in the analysis.

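### The Cox models are said to account for a time-varying fibrinogen-outcome relationship, but as specified they give one window-average hazard ratio, assumed constant and never checked

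*SAP*

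**What the plan says.** Item 1 of Proposed Analyses, in the section on fibrinogen and adverse COPD outcomes, is headed "Assess the time-varying relationship between high fibrinogen and the risk of adverse COPD outcomes". The method is "Cox proportional hazards models will be used to identify hazard risk ratios with corresponding 95% confidence intervals". The SAP then states of these models: "These models will account for the time-varying nature of the relationship between fibrinogen levels and exacerbations/all-cause mortality". The same sentence continues: "as such, they can only be performed in studies that recorded the dates of outcomes of interest".

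The exposure is fixed under Fibrinogen Classification: "four thresholds of baseline fibrinogen will be assessed in these analyses: 250 mg/dL, 300 mg/dL, 350 mg/dL, and 400 mg/dL". It enters each model as one cohort contrast, "the association between high vs. low fibrinogen and a given outcome". The exacerbation model uses events "recorded within 12 months of the initial fibrinogen measurement", and the mortality model uses deaths within 3 years of that same measurement.

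The five model-building steps cover screening of predictors, the 10% change-in-estimate rule, backward selection and a correlation matrix. The output is a set of hazard ratios with confidence intervals for each final model.

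**The concern.** A proportional hazards model with one fixed baseline indicator does not account for a relationship that changes over time. It assumes that the hazard ratio is the same throughout the window. Needing event dates makes an analysis time-to-event; it does not make the effect time-varying. The sentence therefore credits the analysis with a property it lacks, and nothing else in the SAP supplies that property or tests the assumption made in its place.

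This bears on the purpose of the work. The Background says published evidence does not yet support fibrinogen as a biomarker for "increased risk of COPD-related outcomes during a time period that would be relevant to the conduct of a clinical trial". An enrichment claim rests on one baseline sample. A single 3-year ratio cannot distinguish a sample that predicts throughout from one that predicts only early or only late, yet a reader of the SAP is told that the model has dealt with this.

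**Working it through.** **1. Text check.** The SAP gives no numerical result on this point to reproduce, so the check starts from what is specified.

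| Needed for a time-varying effect, or to check proportionality | In the SAP? |
|---|---|
| Fibrinogen-by-time term | No |
| Period-specific hazard ratios | No |
| Schoenfeld residuals or log-log plots | No |
| Fallback if hazards are not proportional | No |
| Comparison of windows | Objectives name 12 and 18 months, and 2 and 3 years; the Cox text sets only 12 months and 3 years |

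The only diagnostic in the model-building steps concerns collinearity. The mention of model assumptions under General Statistical Considerations is about when to pool data and names no check.

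**2. Illustration for death.** From Table 1:
- Deaths within 3 years: 86 + 120 + 220 + 13 + 146 = 585.
- COPD subjects: 1,789 + 1,292 + 2,118 + 145 + 1,032 = 6,376.
- Risk: 585/6,376 = 9.2%.

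Assumptions that are not in the SAP: half the patients are high, the low-group hazard h is constant, nobody is censored before 3 years, there are no covariates, and the yearly hazard ratios r1, r2, r3 are as listed below.

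h solves 0.5(1 − e^(−3h)) + 0.5(1 − e^(−h(r1+r2+r3))) = 585/6,376. All three patterns have r1 + r2 + r3 = 4.5, so h = 0.0257 per year in each.

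The large-sample Cox estimate b solves Σ[d1 − (d1 + d0)·S1·e^b/(S1·e^b + S0)] = 0. Here d1 and d0 are the expected deaths, and S1 and S0 the proportions at risk, in the high and low groups over small time steps.

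| Assumed yearly HRs | Cox HR to 1 year | to 2 years | to 3 years (planned) |
|---|---|---|---|
| 1.5, 1.5, 1.5 | 1.50 | 1.50 | 1.50 |
| 2.2, 1.3, 1.0 | 2.20 | 1.76 | 1.51 |
| 1.0, 1.3, 2.2 | 1.00 | 1.15 | 1.49 |

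The planned estimate is practically the same for all three.

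**3. Could the data show the difference?** In the fading pattern the expected deaths (high, low) are 175.3 and 80.9 in year 1. In year 3 they are 348.3 − 274.4 = 74.0 (from unrounded values) and 236.7 − 159.8 = 76.9.
- SE of the year-1 to year-3 contrast in log HR = √(1/175.3 + 1/80.9 + 1/74.0 + 1/76.9) = 0.211.
- ln(2.2/1.0) = 0.788, so z = 0.788/0.211 = 3.7.
- With 20% high: √(1/79.4 + 1/146.8 + 1/33.1 + 1/138.5) = 0.238, z = 3.3.
- With 80% high: √(1/251.0 + 1/28.9 + 1/106.7 + 1/27.6) = 0.290, z = 2.7.

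A change of that size would be visible with all five cohorts pooled.

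**4. Does it carry into the sample-size step?** That step takes Cox survival estimates at 12 and 36 months, which are the ends of the fitted windows.
- Death, 36 months, half high: the true high-group risk is 1 − e^(−0.02571×4.5) = 10.93%. The Cox-predicted risk is 10.97% (fading) or 10.88% (emerging).
- A second fading pattern, 2.0/1.3/1.0 with h = 0.025: true 1 − e^(−0.025×4.3) = 10.19%, Cox 10.23%.
- Exacerbation, 12 months: Table 1 gives 96 + 236 + 335 = 667 in 1,789 + 1,292 + 2,118 = 5,199, or 12.8% (taken here as COPD subjects with an event). With assumed HRs of 2.0 then 1.0 by half-year and half high, the true high-group risk is 15.23% and the Cox value 15.31%. With 20% high the figures are 17.11% and 17.29%.

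Required numbers scale roughly as 1/risk. The relative errors are 0.04/10.93 = 0.4%, 0.08/15.23 = 0.5% and 0.18/17.11 = 1.1%.

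**The case against.** The best defence is that the sentence explains itself. The clause on event dates suggests that the authors meant only time-to-event, and the Objectives speak of association within cumulative windows, not of year-by-year ratios. On that reading a 12-month or 3-year ratio does address prediction over a trial-length period. This largely stands. It is why the point is a mis-described and unchecked model, not a useless one. It does not rescue the wording, and the constant-ratio assumption remains untested.

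Two planned analyses come close. Kaplan-Meier plots are to be made for each outcome and threshold, but they are described for patients with high fibrinogen and not as a check of proportionality. Stability of fibrinogen is studied in ECLIPSE, but a stable biomarker is not the same thing as a stable hazard ratio.

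It is also fair that the yearly ratios above are invented and that four thresholds cannot all split patients in half. Several stronger conclusions that a reader might draw are not supported:

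- That the hypothetical-trial sample sizes would be wrong. Step 4 of the working shows a negligible error at the planned time points.
- That the Cox hazard ratio is invalid. It averages the association over the window.
- That the association is known to fade. Nothing in the SAP shows this.
- That time-updated fibrinogen should have been used. The SAP says repeated measurements exist only in ECLIPSE, and enrichment uses a single baseline value.

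**Conclusion.** The concern holds in this form: the SAP claims that its Cox models account for change over time, but the specified model assumes no change and the SAP never checks that. Under the assumed patterns, the planned 3-year ratio lies between 1.49 and 1.51 whether the association is steady, absent by year 3 or absent in year 1. The text finding needs no assumptions. The size rests on assumed hazard ratios, a constant low-group hazard, no early censoring, no covariates and full pooling of the five studies; the 3-year ratios are for half the patients high. What is at stake is the interpretation of the main result, not the validity of the average ratio or the sample-size table.

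**What to change.** In Proposed Analyses item 1:

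1. Replace the time-varying wording, in the heading and in the sentence on the Cox models, with time-to-event.
2. For each final outcome model, prespecify a proportionality check of the fibrinogen term: a fibrinogen × log time term or scaled Schoenfeld residuals.
3. Describe the single hazard ratio as an average over the window.
4. Report period-specific hazard ratios at least for the main threshold and wherever proportionality fails. Use years 1, 2 and 3 for death, and 0–6 and 6–12 months for exacerbation, adding 12–18 months if the 18-month window in the Objectives is fitted.

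Period-specific ratios for every model at all four thresholds are not needed, and the sample-size method need not change on this account.

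The cost is SAP text and a few extra PROC PHREG terms on existing data. Intervals widen. In the fading illustration the SE of the log hazard ratio is √(1/348.3 + 1/236.7) = 0.084 over 3 years, against √(1/175.3 + 1/80.9) = 0.134 in year 1 and √(1/74.0 + 1/76.9) = 0.163 in year 3.

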## Objectives

The specific objectives for this analysis are to:

1. Verify the integrity of the integrated database
2. Describe the demographic and clinical characteristics of patients in the integrated database
3. Evaluate methods of defining patients with COPD
4. Assess longitudinal variation in plasma fibrinogen between individuals and within individuals
5. Define a cut point for classifying patients as having high fibrinogen levels
6. Assess the relationship between fibrinogen and risk of mortality and hospitalized COPD exacerbations during relevant time windows

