## General Statistical Considerations

This is a retrospective database analysis of previously collected data from prospective clinical trials and observational studies. These data offer an opportunity to evaluate the relationship between plasma fibrinogen and adverse COPD outcomes by pooling data from multiple sources. Analyses will be conducted separately for individual studies and integrated as indicated. Data will be pooled across the

data sources as deemed appropriate for the analysis being conducted to uphold model assumptions and per variables available within each study.

Adverse COPD outcomes that will be assessed in these analyses include COPD exacerbations and all-cause mortality. The primary endpoint of clinical trials for COPD medications is a hospitalized COPD exacerbation; however, all-cause mortality does hold clinical importance in both the conduct of clinical trials and the overall management of any chronic disease.

As the data are analyzed, some deviation from the analyses outlined is anticipated (e.g., due to missing data; small sample sizes). In instances where these deviations would make the proposed analyses inappropriate, modifications to the analysis plan will be made in consultation with the CBQC and noted in the final report.

SAS statistical software version 9.2 (SAS Institute Inc., Cary, NC) will be used to conduct the analyses. All statistical tests will be two-sided and use a significance level of 0.05 unless otherwise noted. No adjustments for multiple comparisons will be performed unless otherwise noted. For all analyses, missing data will be considered randomly missing, and no data imputations or other algorithms for missing responses will be performed unless otherwise indicated. For certain procedures (such as analysis of variance) subjects with missing data will be excluded from the analysis.

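### The Cox models carry fibrinogen only as high versus low at four cuts with changing reference groups, so they cannot show the shape of the relation on which the cut-point is meant to rest

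*SAP*

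**What the plan says.** The SAP's list of objectives includes: "Define a cut point for classifying patients as having high fibrinogen levels". The Objectives of the section on fibrinogen and adverse outcomes say how this is to be settled: "The nature of the relationship will be critical to the determination of an appropriate cut-point or threshold".

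The section Fibrinogen Classification fixes the candidates: "four thresholds of baseline fibrinogen will be assessed in these analyses: 250 mg/dL, 300 mg/dL, 350 mg/dL, and 400 mg/dL". It gives their origin separately, as follows: "Based on preliminary analyses of the distribution of fibrinogen among patients with COPD". In the same section, a patient's label as high or low depends on the cut in use, since the wording is that "fibrinogen will refer to the level of fibrinogen in relation to the threshold(s) being assessed in the analysis"; the comparison group is thus redefined at each threshold.

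In Proposed Analyses, the exposure in the Cox models is a high-versus-low cohort term, fitted at each threshold: "Analyses will be conducted using the fibrinogen thresholds determined previously (250 mg/dL, 300 mg/dL, 350 mg/dL, and 400 mg/dL". Covariates enter partly by whether they change that high/low effect by at least 10%. No continuous, spline or ordered-band fibrinogen term is specified for these models, and no rule is stated for preferring one threshold.

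On error control, General Statistical Considerations says: "All statistical tests will be two-sided and use a significance level of 0.05 unless otherwise noted". On multiplicity, the same section adds: "No adjustments for multiple comparisons will be performed unless otherwise noted". No adjustment is noted for the thresholds.

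**The concern.** The plan relies on the shape of the relation but specifies Cox models that do not estimate shape. A high/low contrast gives one number per cut. The four numbers are not points on a curve, because the low group grows from everyone below 250 mg/dL to everyone below 400 mg/dL. The 10% rule is applied to a different contrast each time, so the adjustment set may also differ between thresholds.

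A smooth rise in risk with no threshold would still give four hazard ratios above 1, one of them largest and one with the smallest p-value, not necessarily the same one. With no stated criterion, the cut-point could be a product of how the results are read. The same data would then both choose the cut and supply its hazard ratio, which biases that ratio upwards. For a marker meant to enrich trial populations, the location of the cut and the risk contrast at it are the quantities that matter.

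**Working it through.** The SAP gives no error rate or performance figure for choosing the cut-point, so there is none to reproduce.

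**Inputs from Table 1.** Hospitalized exacerbations within 12 months: 96 + 236 + 335 = 667 in 1,789 + 1,292 + 2,118 = 5,199 COPD subjects (ARIC, CHS, ECLIPSE). Deaths within 3 years: 86 + 120 + 220 + 13 + 146 = 585 in 5,199 + 145 + 1,032 = 6,376.

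**Assumptions.** The SAP gives neither the fibrinogen distribution nor an effect size for these data. The main scenario puts 90/70/45/25% of patients above 250/300/350/400 mg/dL, with a log-linear effect of HR 1.2 per SD and no threshold. As a range, lognormal fibrinogen with mean 330 (CV 0.20), 380 (CV 0.22) or 430 mg/dL (CV 0.22) and HR 1.3 per 100 mg/dL was also used.

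**Step 1: hazard ratios that a smooth relation produces.** For a standardised marker cut at c and β = ln 1.2 = 0.182, the ratio of mean hazards is [(1 − Φ(c − β))/(1 − Φ(c))] ÷ [Φ(c − β)/Φ(c)]. With 90% above the cut, c = −1.282 and Φ(c − β) = 0.0716, so the ratio is (0.9284/0.90) ÷ (0.0716/0.10) = 1.44. The four cuts give 1.44, 1.36, 1.34 and 1.36.

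Under the lognormal scenarios:

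| Assumed mean (mg/dL) | 250 | 300 | 350 | 400 |
|---|---|---|---|---|
| 330 | 1.36 | 1.32 | 1.34 | 1.42 |
| 380 | 1.54 | 1.44 | 1.42 | 1.45 |
| 430 | 1.74 | 1.59 | 1.51 | 1.49 |

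The underlying relation is the same in each row, yet the largest ratio falls at 400 in the first and at 250 in the other two.

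**Step 2: which cut is preferred.** In samples of 5,199 with about 667 events under the main scenario, the largest hazard ratio picks 250 in about 55% and the smallest p-value picks it in about 4%. With mean 380 and HR 1.3 per 100 mg/dL, the largest ratio picks 250 in 55% and the smallest p-value picks 400 in 73%.

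**Step 3: overstatement at the chosen cut.** This is the mean of the estimated over the true hazard ratio at the chosen cut, in the main scenario:

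| Sample size | Largest HR chosen | Smallest p chosen |
|---|---|---|
| 5,199 (pooled) | about 8% | about 6% |
| 2,118 (ECLIPSE) | about 15% | about 11% |

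**Step 4: no association.** Four independent tests would give 1 − 0.95⁴ = 0.185. The nested cuts are correlated; simulation at the Table 1 totals gives about 0.16 for at least one p < 0.05, per outcome and population.

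**Step 5: one fixed reference.** With HR 1.3 per 100 mg/dL, bands compared with below 250 give about 1.14, 1.29, 1.46 and, for 400 and above, 1.77 to 2.00 depending on the distribution. The gradient is visible here, whereas the changing-reference ratios in Step 1 hide it.

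**The case against.** The strongest reply is that this is not an open search for a cut. Four round values were fixed from the distribution of fibrinogen, not from outcomes, and results are planned for all four. Nothing says that the largest hazard ratio or the smallest p-value decides. For enrichment, above versus below a given entry cut is also the relevant contrast, so changing reference groups follow from the purpose. All of that stands. It bounds the inflation and justifies keeping the four contrasts, but it does not supply a rule or let those contrasts show shape.

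Three stronger readings are tempting, and the SAP does not support them.

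- A reader might infer that fibrinogen is never analysed without a threshold. The section on key assumptions plans a Kolmogorov-Smirnov comparison of the whole baseline distribution between patients with and without each outcome, and its histograms help to inform the threshold. A logistic model there may use fibrinogen as continuous, though its coding is not stated and that section disclaims finding the final threshold. The Kolmogorov-Smirnov test is unadjusted and gives neither an effect estimate nor a shape, so the gap in the Cox models remains.
- A reader might infer that there is no check across data sources. Analyses are planned by study as well as pooled, and robustness across studies is a stated reason for integration. What is missing is a validation role or criterion for the cut-point.
- A reader might compound the error rate over both outcomes and both populations. The plan does not declare success on any single p-value, and the size of the second population (ECLIPSE patients with prior exacerbations) is not given.

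Finally, at HR 1.2 per SD more than 99% of pooled samples reach p < 0.05 at some cut. False positives are therefore secondary to the location of the cut and the bias at it.

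**Conclusion.** The point holds for the Cox models and the choice of cut-point. As specified, the four hazard ratios cannot show the form of the relation or locate a threshold, and the cut preferred would depend on a criterion the SAP does not state. In the main scenario the hazard ratio at a cut chosen in the same data is overstated by about 6 to 8% pooled and 11 to 15% at ECLIPSE size. With no association, the chance of p < 0.05 at one or more cuts is about 16% per outcome and population.

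These sizes rest on the assumed distribution and effect. The overstatement also assumes selection by largest hazard ratio or smallest p-value, neither of which the SAP adopts. That the dichotomised models cannot show shape does not depend on these assumptions. This is a change that should be made; it does not make the planned analyses unusable.

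**What to change.** In Proposed Analyses, under the Cox models:

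1. For each outcome, add a Cox model stratified by study, with log-fibrinogen as a continuous term and a restricted cubic spline for shape, using one common covariate set. Make it the main test of association and the basis for describing the relation.
2. Keep all four thresholds as enrichment contrasts, with the same covariate set, and show the absolute risk above and below each.
3. State in advance the rule by which the cut-point will be chosen.
4. Report the hazard ratio and risks at the chosen cut with bootstrap or leave-one-study-out correction.

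No new data are needed. The cost is a continuous and spline model per outcome and a resampling or leave-one-study-out run, and the reported hazard ratio at the cut-point is likely to be slightly smaller.

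### The Kaplan-Meier analysis of risk over time covers only high-fibrinogen patients, so it gives no observed high-versus-low contrast, and the 18-month and 2-year associations have no analysis assigned to them

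*SAP*

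**What the plan says.** The item appears in the SAP under Relationship Between Fibrinogen and Risk of Adverse COPD Outcomes, Proposed Analyses, directly after the Cox modelling steps.

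- Aim: "Assess the relation between high fibrinogen and the risk of adverse COPD outcomes over time".
- Population: "Time-to-event analyses will be performed using survival analysis methods for patients with high fibrinogen in studies which recorded dates". The studies are ARIC, CHS and ECLIPSE for hospitalized exacerbations, and all five studies for death.
- Plots: "PROC PHREG will be used to create Kaplan Meier plots for each outcome, and plots will be repeated for each threshold assessed".
- Other output: "Means, standard deviations, medians, and ranges of time-to-events will also be calculated".

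The Objectives of the same chapter carry the same restriction: "Assess the time-to-event (COPD exacerbation and/or all-cause mortality) among patients with high fibrinogen". They also set the time points for the association: 12 and 18 months for exacerbations, 2 and 3 years for mortality.

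Under Fibrinogen Classification, the words high and low "refer to the level of fibrinogen in relation to the threshold(s) being assessed in the analysis", with thresholds of 250, 300, 350 and 400 mg/dL.

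The Cox section treats the population differently. Of its univariate step it says: "These models will be fitted on data of patients with high and low fibrinogen". The effect it estimates is described as "the association between high vs. low fibrinogen and a given outcome".

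**The concern.** A relation needs at least two groups or a graded exposure. This item names one group, the patients above the threshold, and it names no curve, stratum or test for those below. Read as written, it describes how soon events occur in high-fibrinogen patients. It cannot show whether they occur sooner or more often than in low-fibrinogen patients from the same studies.

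This matters because these plots are the SAP's only planned display of observed risk over time. Among the Cox results, only hazard ratios with confidence intervals are listed for presentation. A reader judging fibrinogen as an enrichment marker will want to see the observed risk on each side of a threshold, and whether the gap holds, narrows or reverses during a trial-length follow-up. The Cox section says its models account for a relationship that varies with time, but it specifies neither a check of proportional hazards nor a time-interaction term. High-only curves cannot fill that gap.

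**Working it through.** The SAP states no figure for this analysis, so the main check compares its parts.

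**1. Population against aim.** The item's aim is a relation and its population is the high group alone. For a threshold c, the item yields the event-free probability S_high(t; c). A high-versus-low risk difference is S_low(t; c) − S_high(t; c), and S_low is not among the outputs.

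**2. Does repeating the plot by threshold supply a comparator?** Everyone above 400 mg/dL is also above 350, 300 and 250 mg/dL. The four groups are nested, and the group above 250 contains the other three. Comparing their curves sets a subset against a larger set that includes it. This can suggest a trend, but it is not a high-versus-low contrast at any threshold.

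**3. Is it a slip in one place?** The bullet under Objectives has the same restriction. Another bullet in that list, and the first Cox step, name both groups where both are meant.

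**4. Which promised time points have a high-versus-low analysis?**

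| Association promised under Objectives | Cox analysis | Kaplan-Meier item as written |
|---|---|---|
| Exacerbation, 12 months | yes | high group only |
| Exacerbation, 18 months | no, outside the 12-month window | high group only |
| Death, 2 years | no separate estimate; inside the 3-year window | high group only |
| Death, 3 years | yes | high group only |

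Two of the four have no high-versus-low result of their own. The 2-year mortality association could be read off the 3-year model only by assuming a constant hazard ratio, and high-only curves cannot check that assumption.

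**5. Illustration of what the missing curve would show.** SAP Table 1 gives 335 hospitalized exacerbations within 12 months and 2,118 COPD subjects for ECLIPSE: 335/2,118 = 15.8%. Assumptions: the 335 are patients, all among the COPD subjects (the column does not say so); a fraction f is high; and the hazard ratio h is constant. Solve f·[1 − (1 − p_low)^h] + (1 − f)·p_low = 0.158, with p_high = 1 − (1 − p_low)^h.

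| h | f | p_high | p_low | Difference (points) |
|---|---|---|---|---|
| 1.3 | 0.10 | 19.5% | 15.4% | 4.1 |
| 1.3 | 0.25 | 18.8% | 14.8% | 4.0 |
| 1.3 | 0.75 | 16.7% | 13.1% | 3.6 |
| 2.0 | 0.10 | 27.0% | 14.6% | 12.5 |
| 2.0 | 0.25 | 24.3% | 13.0% | 11.3 |
| 2.0 | 0.75 | 17.9% | 9.4% | 8.5 |

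The values of f and h are assumed. The table only shows the scale of a contrast that the high-only plot leaves out, and the point does not depend on it.

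**The case against.** The strongest reply is that the relation is assessed elsewhere. The Cox models use both groups at all four thresholds and give hazard ratios with confidence intervals. The outcome-stratified histograms, with the Kolmogorov-Smirnov test, also compare fibrinogen between patients with and without events. This stands. A reader might infer from the high-only wording that the SAP never compares high with low fibrinogen, and the documents do not support that.

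A reader might also infer that the enrichment calculation is compromised. It is not: the sample-size step takes its survival estimates from the Cox models, not from these plots.

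The restriction may be shorthand. The Cox item also speaks only of high fibrinogen in its title yet uses both groups, and plots repeated by threshold would suit two-group curves. That is possible. But the wording limits the population explicitly, the Objectives repeat it, and both groups are named elsewhere when meant. A plan should not leave this to be guessed.

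The low-group risk could be recovered by subtraction from the overall risk and the fraction high. At 12 months for exacerbation and 3 years for death, where Table 1 gives counts, this is roughly so. It does not provide 18-month or 2-year values, confidence intervals or a curve, and the SAP schedules no such step.

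Finally, a reader might take the naming of PROC PHREG, a Cox-model procedure, to mean that the curves will be model-based and forced to be proportional. That follows only if fibrinogen or other covariates enter the model. The SAP calls the plots Kaplan-Meier, and a fit without covariates, stratified by group, would give unadjusted curves. The covariates listed for consideration under the item leave this open, so it needs a clarifying sentence; it is not a separate error.

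**Conclusion.** The point holds for this one analysis. As written, the time-to-event item cannot deliver the relation in its title, because it has no low-fibrinogen group and the four high groups are nested. The SAP's overall objective, its Cox inference and its sample-size work are intact.

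The loss is the observed high-versus-low comparison of risk over time: two of the four promised associations have no result of their own, and no plot can show crossing or converging risks. This rests on reading the population statement literally, as the Objectives support. If two-group curves were always intended, the defect is one of wording, and most of the same correction applies. It should be corrected before the analyses are run.

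**What to change.** 1. In the time-to-event item and the matching bullet under Objectives, widen the population from the high group to the high and low groups, both defined at the threshold being assessed.
2. For each outcome and threshold, produce unadjusted Kaplan-Meier curves for both groups, and state that no covariates enter the model and that the fit is stratified by group.
3. Report each group's risk and the risk difference with 95% CI at 12 and 18 months for hospitalized exacerbation and at 2 and 3 years for death. Where studies are pooled, stratify by study.

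The choice of SAS procedure, a curve for all COPD patients and a log-rank test are optional. A log-rank test would largely duplicate the unadjusted Cox comparison.

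The cost is a change of wording in two places and a modest amount of extra output. No new data are needed, because the low-fibrinogen patients are already in the Cox models.
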